10.3.3	Cost and cost-effectiveness study.....	79
10.4	Confidentiality.....	79
10.4.1	Pragmatic cluster RCT.....	79
10.4.2	Other mixed methods studies.....	79
10.4.3	Linking between pragmatic cluster RCT and mixed methods studies	80
10.4.4	Cost and cost-effectiveness study.....	80
10.5	Risk and benefits to participants.....	81
10.6	Access to data.....	81
10.7	Dissemination policy	81
11	References	84
12	Appendix	91
12.1	Informed consent forms appended to the protocol	91
12.2	Study instruments appended to the protocol	91
12.3	Budget and collaboration appended to the protocol.....	92
12.4	TIMCI Preliminary Theory of Change.....	93

Abbreviations

(co)-PI	(co)-Principal Investigator
(e)CRF	(electronic) Case Report Form
ASHA	Accredited Social Healthcare Activist
BI	Burnet Institute
CDSA	Clinical Decision Support Algorithm
CE	Conformité Européenne
CG	Caregiver
CHC	Community Health Center
CS	Case Studies
CSO	Civil Society Organization
DALY	Disability-Adjusted Life Years
DB	Database
DHIS	District Health Information System
DHS	Demographic And Health Surveys
DMC	Data Monitoring Committee
DMP	Data Management Plan
EDC	Electronic Data Capture
ePOCT	electronic Point of Care Tool
ERC	Ethical Review Committee
FGD	Focus Group Discussion
GCP	Good Clinical Practice
GPS	Global Positioning System
HC	Health Center
HCP	Health Care Provider
HMIS	Health Management Information System
HMSC	Health Ministry's Screening Committee
HP	Health Post
HQ	Headquarters
IAG	International Advisory Group
ICC	Intercluster Correlation Coefficient
ICD-10	International Statistical Classification of Diseases and Related Health Problems
ICH	International Council for Harmonisation (of Technical Requirements for Pharmaceuticals for Human Use)
ICMR	Indian Council of Medical Research
ID	Identification
IDI	In-Depth Interview
IEC	Institutional Ethics Committee
IHI	Ifakara Health Institute
IMCI	Integrated Management of Childhood Illnesses
IQR	Interquartile Range
IRB	Institutional Review Board
KGMU	King George's Medical University
KII	Key Informant Interview
LMIC	Low- and middle-income countries
M&E	Monitoring and Evaluation
MedAL-C	Medical Algorithm - Creator
MedAL-R	Medical Algorithm - Reader

MedDRA	Medical Dictionary for Regulatory Activities
MEP	Monitoring and Evaluation Plan
MIS	Management Information System
MOH	Ministry Of Health
NHM-UP	National Health Ministry – Uttar Pradesh
NIMR	National Health Research Ethics Committee
NRRC	National Research Registration Committee
PHC	Primary Healthcare Center
PII	Personal Identifiable Information
QoC	Quality of Care
RA	Research Assistant
RCT	Randomised controlled trial
RHC	Rural Health Center
SAP	Statistical Analysis Plan
SNOMED CT	Systemized Nomenclature of Medicine - Clinical Terms
SOP	Standard Operating Procedure
SPA	Service Provision Assessment
SRA	Stringent Regulatory Authority
Swiss TPH	Swiss Tropical and Public Health Institute
TIMCI	Tools for integrated management of childhood illness
ToC	Theory of Change
UCAD	Université Cheikh Anta Diop de Dakar
UoN	University of Nairobi
US FDA	United States Food and Drug Administration
VPN	Virtual Private Network
WHO	World Health Organisation

1 Summary

Background / rationale

Achieving global targets for child mortality reduction in low- and middle-income countries (LMICs) requires significant improvements in the detection and management of severely ill children. Existing guidelines are inconsistently implemented by healthcare providers and, as they are based on clinical signs, are inadequate for the detection of hypoxaemia, a strong predictor of mortality.

The overall goal of the Tools for the Management of Childhood Illness (TIMCI) project is to reduce morbidity and mortality in sick children attending primary care facilities, while supporting the rational and efficient use of diagnostics and medicines by healthcare providers. The evaluation component of the project seeks to generate evidence on the health impact, operational priorities, cost and cost-effectiveness of introducing pulse oximetry, alone or embedded into a Clinical Decision Support Algorithm (CDSA), at primary care level in LMICs, for children 0 – 59 months of age, to facilitate national and international decision-making on scale-up.

Study design

Health and quality of care impact are evaluated through pragmatic, parallel group, cluster randomised controlled superiority trials in India and Tanzania, and quasi-experimental pre-post studies in Kenya and Senegal.

In the pragmatic cluster randomised controlled trial (RCT), primary care facilities (clusters) are randomly allocated (1:1) to pulse oximetry or control in India, and (1:1:1) to pulse oximetry plus CDSA, pulse oximetry, or control in Tanzania..

The intervention package will be piloted and refined over a 3-month period prior to the start of the definitive pragmatic cluster RCT.

This will be complemented by embedded mixed methods sub-studies to evaluate key components of quality of care and gain a deeper understanding of the implementation processes, mechanisms and context following a realist approach. These studies include modified Service Provision Assessments (SPAs), a facility-based process mapping and time-flow study, qualitative studies with caregivers, healthcare providers and key stakeholders, a survey sent to selected key stakeholders on a quarterly basis, a desk-based project document and monitoring and evaluation (M&E) review, and a cost and modelled cost-effectiveness study.

Study setting

The study setting encompasses facility-based primary care level in three districts of Uttar Pradesh in India (Unnao, Sitapur, and Deoria) and in three councils in Tanzania (Mwanza, Tanga and Tabora). Caregivers often attend different types of facilities to meet their primary care needs; the study setting therefore includes a diverse range of facilities providing primary care services, including outpatient settings within larger health centres in addition to the more

traditionally-labelled primary care facilities. This includes primary healthcare centres (PHCs) and community health centres (CHCs) in India and dispensaries and health centres (HCs) in Tanzania.

Key Eligibility Criteria

Consenting government-designated healthcare facilities providing outpatient curative primary care services for children 0 – 59 months of age will be included. Facilities will be excluded if they use pulse oximetry as a routine part of outpatient consultations of children prior to the start of the intervention.

Children 0 – 59 months, for whom caregivers provide consent, will be eligible if attending any study facility with an illness, excluding those admitted as inpatients within the facility, or attending for a consultation related to trauma only.

Caregivers of enrolled children, and healthcare providers at study sites involved in the care of children 0 – 59 months of age, and stakeholders involved in or affected by the intervention, will be eligible for inclusion in the applicable studies.

Interventions

The TIMCI project will introduce pulse oximetry, alone or embedded into a CDSA, into primary care facilities, supported by targeted training and embedded into monitoring, supportive supervision and maintenance systems. Refresher training will be provided to healthcare providers in the routine care arm.

The pulse oximeters provided in the study will be UNICEF-approved handheld pulse oximeters with paediatric and neonatal probes. Healthcare providers will be provided with guidance (paper-based, or within the CDSA) and trained on the following criteria for pulse oximetry use:

- All children under 2 months of age
- Children 2 – 59 months of age presenting with cough / difficulty breathing
- Children 2 – 59 months of age with Integrated Management of Childhood Illness (IMCI) signs of moderate / severe disease (IMCI 'yellow' or 'red' classification)

Healthcare providers will be advised to use a cut-off of $\text{SpO}_2 < 90\%$ for referral, unless specific national guidance states otherwise. Different SpO_2 cut-offs for referral for sites at high altitude will be finalised with the International Advisory Group (IAG) and Ministries of Health (MoHs).

The tablet-based CDSA, provided to facilities in arm 1, guides healthcare providers through medical consultations with an algorithm called electronic point-of-care tool (ePoct+). The clinical algorithm will be adapted to reflect national guidelines for the management of children 0 – 59 months of age in primary care (based on IMCI and additional relevant case management guidelines), and will be validated through consultation of international and national experts in each country.

Outcomes

Two primary outcomes will be assessed in order to improve the ability to detect a difference between each of the intervention arms (pulse oximetry alone, or embedded into a CDSA) and the control arm, given the relatively low occurrence of severe outcomes at primary care level:

- Proportion of children with a severe complication (death or secondary hospitalisation) by Day 7
- Proportion of children admitted to hospital within 24 hours of the Day 0 primary care consultation and as a result of a referral

Important secondary and other outcomes include:

- Proportion of children with severe complication (death or secondary hospitalisation) by Day 28
- Proportion of children cured (defined as caregiver reported recovery from illness) at Day 7 follow-up
- Proportion of children referred by a primary care healthcare provider to a higher level of care (either to a hospital or to an inpatient part of a larger primary healthcare facility) at Day 0 consultation
- Proportion of children who completed referral, as reported at day 7 follow-up
- Proportion of children with hypoxaemia (according to differing cut-offs) with severe complication
- Proportion of children prescribed an appropriate antibiotic at Day 0 consultation

Sub-group analyses will include age (under 2 months, 2 – 12 months, 13 – 59 months), sex, and clinical presentation (with cough / difficulty breathing, fever, other). Other exploratory analysis will be conducted of individual and health system factors associated with health and patient-centred outcomes.

Mixed methods sub-studies will mostly be exploratory, to evaluate quality of care outcomes and explore perceptions, values, attitudes and beliefs. Process evaluation criteria will be evaluated according to the Medical Research Council criteria.

Cost and modelled cost-effectiveness will assess:

- Full implementation cost of the intervention per focal country (cost to health system as well as direct costs paid by the household to the health system)
- Cost per child assessed using pulse oximetry devices and CDSA per country; where applicable, compared to cost per child in routine care
- Modelled cost per DALY averted attributed to the introduction of pulse oximetry and CDAs

Sample size

The sample size for the pragmatic cluster RCT is calculated separately for each country to compare each of the intervention arms with the control arm. In order to detect a 30% reduction in the severe complication primary outcome (from 1.1% to 0.77%) with 80% power, we estimate a sample size in each country as follows:

- India – Initial sample size calculation for the three arm trial was 0 facilities per arm, recruiting an average of 510 children over the 12 month period, with an average of 110 per CHC per month and 20 children per PHC, and a facility ratio of CHC : PHC of 1:3, equating to 20,400 children per arm over the study. Following the decision not to introduce the CDSA plus pulse oximetry arm, a decision was made to reallocate facilities to the remaining two arms up to 60 facilities per arm.
- Tanzania – 22 facilities per arm, recruiting an average of 1680 children over the 12 month period, with an average of 350 per health centre per month and 70 per dispensary per month, and an average ratio of health center : dispensary of 1:3, equating to 36,960 children per arm over the study

Service provision assessments and process mapping will be conducted in 6 facilities per arm per country, stratified by rural / urban location and facility type, at 5 time points (once per quarter in each facility). At each facility at each time point, 10 – 30 children per facility will be included, resulting in an estimated sample size of 600 clinical observations, time-flow observations and exit interviews per arm in each country over the study period.

Final sample size for qualitative studies will be determined by reaching thematic saturation. Per country, an estimated total of 70-90 in-depth interviews (IDIs), 6 – 8 walking interviews and 12 focus group discussions (FGDs) will be conducted with caregivers, spread across the study period. Similarly, 70-90 IDIs and 12 FGDs will be conducted with healthcare providers, and approximately 45-55 key informant interviews with stakeholders.

Ethics Review

Following independent scientific merit review, the protocol will be submitted to all relevant research ethics committees / institutional review boards in each country and the WHO ethical review committee.

Estimated study timeline

Pending all relevant ethical approvals, first enrolment is anticipated to be in January 2021, with completion of data collection in March 2022.

Depending on the evolution of the Covid-19 pandemic, we will keep implementation, research processes and timelines under review and inform the necessary bodies and institutions accordingly of any possible adaptations.

2 General information

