8.3.3 Cost and cost-effectiveness study

When all the cost components have been collected, the data will be aggregated or collated in Excel. Once the summary is completed, a cost profile of the programme activities will be derived and after the total costs of the programme have been calculated, the unit costs will then be derived (i.e. total costs divided by the sample size). These profiles are useful in highlighting major cost components (and thus identifying potential areas where improvements in efficiency may have significant impact on costs). For this evaluation, analysis will focus on full costing and incremental costing approach. Total, average and incremental costs per year will be estimated. Costs associated with increasing the oxygen saturation referral threshold will be estimated based on the additional proportion of children meeting referral criteria.

When available, effectiveness data will be combined with the cost data and cost per DALY averted will be estimated. Effectiveness will be modelled using the information on severe outcomes such as mortality, and secondary hospitalization, adjusting as far as possible the level of severity of illness of the child at presentation.

At primary care facilities, these will include measurements (when taken by healthcare providers) such as anthropometry, respiratory rate, temperature and routine investigations where available (e.g. haemoglobin, CRP), and oxygen saturation (post-intervention/in intervention arms). We will also use diagnosis and severity classification recorded by primary care providers.

At hospital level, we will also utilize the same measurement data, and other vital sign data (such as a paediatric early warning score if recorded), decision to admit, intensive care and / or ventilation, provisional and final diagnosis, admission outcome (discharge, death, left against medical advice) and length of hospital stay. We will then use these indicators, along with mortality from phone call follow-up data by Day 28, to predict probability of mortality based on available literature. The DALY calculation will be based primarily on probability of mortality

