over a relatively short horizon (to be determined based on a review of literature, likely between three and six months to reflect the time windows used in post hospital discharge mortality studies). The types of illnesses considered do not typically lead to long-term disability, and the duration of illness is too short to have a big impact on DALY calculations. We will not use age weights: we will use GBD (2017) DALYs,⁶⁰ and we will not use country-specific disutility data, both since we are unsure these exist for all the countries, and they render cross-country comparisons more difficult.

Sensitivity analysis

As not all data will be available precisely, we will explore possible assumptions using sensitivity analysis which will assess how the estimates would react to percentages changes in the value of the assumptions. It can help the reviewer to determine which parameters are the key drivers of a model's results. Guidelines and standard textbook recommend that economic evaluations should include sensitivity analysis.⁶¹ We will undertake one-way sensitivity analysis of key parameters using the major outcome and cost parameters. Typically, such analyses are more sensitive to the assumptions about outcomes, and for this we have to rely on the best judgement of the epidemiologists.

9 Monitoring

All studies will be conducted in accordance with the protocol and international and applicable national regulatory requirements. The pragmatic cluster RCT will be monitored in accordance with ICH Good Clinical Practice in addition to the aforementioned requirements. Independent trial monitoring will be conducted by the Clinical Operations Unit within the Department of Medicine at Swiss TPH (separate unit from lead investigators). The Clinical Operations Unit will be responsible for setting up and carrying out the monitoring of trial conduct using a risk-based approach, combining on-site, remote and centralised monitoring.

On-site monitoring will be done for a random selection of sites and can be triggered in addition for sites appearing to be breaching. Screening data, consent, recruitment rates and missing data on primary and important secondary endpoints will be reviewed remotely. Findings of remote monitoring may influence on-site monitoring.

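### No planned step carries the trial's clustered sampling error into the cost per DALY averted, so its reported range is likely to be too narrow unless the effect is varied at least as widely as the trial's 95% CI

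*Protocol*

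**What the plan says.** The Protocol summary names the outcome: "Modelled cost per DALY averted attributed to the introduction of pulse oximetry and CDAs". Protocol 8.3.3 states: "When available, effectiveness data will be combined with the cost data and cost per DALY averted will be estimated". Section 6.4.4 says that the model uses each arm's proportions referred to hospital on Day 0 or by Day 7, or with secondary hospitalisation by Day 28. Section 8.3.3 adds hospital indicators and Day 28 deaths, used "to predict probability of mortality based on available literature", and says: "The DALY calculation will be based primarily on probability of mortality".

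The plan for uncertainty is the short sensitivity paragraph that closes 8.3.3. The analysis will "assess how the estimates would react to percentages changes in the value of the assumptions", and then: "We will undertake one-way sensitivity analysis of key parameters using the major outcome and cost parameters". The paragraph observes that such results usually depend most on the outcome assumptions, and continues: "for this we have to rely on the best judgement of the epidemiologists". It gives no percentages.

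Section 5.8 adds a most-likely cost scenario with a discussion of cost drivers. Section 8.3 refers statistical detail to the SAP, which has no economic analysis. Neither document plans a probabilistic analysis, a bootstrap, an interval for the ratio or an acceptability curve. The trial analysis itself (Protocol 8.3.1, SAP 6.2.1) will report risk differences with 95% CIs from models with facility as a random effect.

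**The concern.** Several inputs to the ratio are estimates from a cluster trial. Their sampling error will be known, yet no planned step uses it. Changing one input at a time by a chosen percentage shows which inputs matter. It does not show how uncertain the ratio is, how cost and effect vary together, or how likely it is that the intervention averts no DALYs.

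Cost-effectiveness is a stated objective (Protocol section 4), and the evaluation is meant to inform national and international decisions on scale-up. As written, a ratio built on an imprecise or non-significant effect could be published with a tight range.

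**Working it through.** The documents state no range for the ratio, so there is none to reproduce. The check reproduces the sample size, then asks how much sampling error that design leaves in one effect.

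**Inputs.** Severe complication by Day 7 of 1.1% v 0.77% (Protocol summary). Two-sided 5% level, 80% power and ICC 0.001 (Protocol 6.6.1; sidedness from SAP 4.1). Tanzania: 22 facilities per arm × 1,680 children. India: initially 40 × 510, now up to 60 facilities per arm; I assume that 510 per facility still holds.

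**Reproducing the sample size.** The two-proportion formula without continuity correction gives 13,351 per arm before clustering.
- India: design effect 1 + 509 × 0.001 = 1.509; 13,351 × 1.509 = 20,147, or 39.5 facilities, rounded up to 40 (20,400 children, as stated).
- Tanzania: design effect 1 + 1,679 × 0.001 = 2.679; 13,351 × 2.679 = 35,767, or 21.3 facilities, rounded up to 22 (36,960 children, as stated).

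**Sampling error of the effect.** Suppose that the planned difference, 3.3 per 1,000, is observed.
- n_eff = children per arm / design effect.
- SE = √[(0.011 × 0.989 + 0.0077 × 0.9923) / n_eff] = √(0.01852 / n_eff).
- With cost held fixed, cost per severe complication averted is proportional to 1/(risk difference), so its multipliers are 3.3/upper limit and 3.3/lower limit.

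For the stated facility mix (one larger facility to three smaller), I approximate random-effects weighting by n_eff = Σ m/[1 + (m − 1) × 0.001].
- Tanzania: health centres 350 × 12 = 4,200, dispensaries 70 × 12 = 840. n_eff = 5.5 × 4,200/5.199 + 16.5 × 840/1.839 = 11,980.
- India: CHCs 110 × 12 = 1,320, PHCs 20 × 12 = 240. n_eff = 15 × 1,320/2.319 + 45 × 240/1.239 = 17,255.

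| Design, per arm | n_eff | SE per 1,000 | 95% CI per 1,000 | Multiplier |
|---|---|---|---|---|
| Tanzania, 22 equal facilities | 13,796 | 1.16 | 1.03 to 5.57 | 0.59 to 3.2 |
| Tanzania, stated mix | 11,980 | 1.24 | 0.86 to 5.74 | 0.58 to 3.8 |
| India, 60 equal facilities | 20,278 | 0.96 | 1.43 to 5.17 | 0.64 to 2.3 |
| India, 60 facilities, stated mix | 17,255 | 1.04 | 1.27 to 5.33 | 0.62 to 2.6 |

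**A smaller effect.** If Tanzania observed a 20% reduction (1.1% v 0.88%, equal facilities), SE = √[(0.011 × 0.989 + 0.0088 × 0.9912)/13,796] = 1.19 per 1,000. The CI is −0.14 to 4.54 and includes zero, so the ratio has no finite upper limit.

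**One-way comparison (percentages assumed).** Changing the effect by ±20% gives 1/1.2 = 0.83 to 1/0.8 = 1.25 times. ±30% gives 1/1.3 = 0.77 to 1/0.7 = 1.43 times. With equal facilities, matching the trial CI needs about ±57% in India (1.96 × 0.956/3.3) and ±69% in Tanzania (1.96 × 1.159/3.3).

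**The case against.** The strongest reply is that the plan states no range, so none can be called too narrow. A judged change of about ±70% would span 0.59 to 3.3 times, much the same as the trial's own interval in Tanzania, and nothing forbids using the trial CI as the one-way range. The sentence about judgement may also refer mainly to the step from trial indicators to mortality, which the trial does not estimate. Both points stand. A reader might infer that the published range is bound to be far too narrow, or that judgement is sure to replace the trial's error. The text supports neither.

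Three inferences about size also go too far.
- A reader might take the multipliers as those of the cost per DALY averted. They are for Day 7 severe complications; the DALY model uses other arm proportions and predicted mortality.
- A reader might add that deaths are rarer, so the DALY interval must be wider still. That would follow if DALYs came from counted deaths. They rest primarily on predicted probabilities, whose sampling variance need not match.
- The usual design effect for unequal clusters in Tanzania (CV² = 0.75, giving 1 + (1.75 × 1,680 − 1) × 0.001 = 3.939) gives an upper multiplier of 6.0. It assumes weighting by facility size. The planned random-effects model gives large facilities less weight, hence about 3.8.

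It can also be said that the trial report will show the imprecision of the effect, and that a pooled two-country effect would be more precise. Neither puts that uncertainty into the ratio that decision-makers will read.

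**Conclusion.** The gap is real and worth correcting. Section 8.3.3 offers only one-way variation of unspecified size, and no passage carries the clustered sampling error of the trial-estimated inputs into the cost per DALY averted or varies cost and effect jointly. Whatever percentages are chosen, varying one input at a time cannot show joint uncertainty or give the probability of no benefit.

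The range is likely, not certain, to be too narrow: it is so if the effect is varied by less than the trial CI. The figures assume that the planned effect is observed, ICC 0.001, complete follow-up and fixed cost. They leave out uncertainty in costs, which come from eight facilities per country (Protocol 6.6.3), and in the literature-based mortality step. They illustrate scale and are not an interval for the DALY ratio.

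**What to change.** In Protocol 8.3.3, add a probabilistic sensitivity analysis.
- Draw every trial-estimated input (arm proportions referred, with secondary hospitalisation, and dead by Day 28) from its cluster-adjusted estimate and standard error, or from a bootstrap of facilities applied to the trial outcomes only. Do not bootstrap costs by facility: eight costed facilities per country are too few to resample within arm and stratum.
- Draw these inputs jointly with stated distributions for the cost and literature mortality inputs.
- Report the differences in cost and in DALYs with 95% intervals, and the cost-effectiveness plane or net benefit with an acceptability curve. These remain defined when the effect CI includes zero; an interval for the ratio does not.
- Keep one-way analysis as a supplement and for inputs that the trial does not estimate, and state the range used for each.

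The cost is protocol wording and some programming, with no new data. The reported interval will probably be wider and may include no benefit.
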